8.2 Definitions

8.2.1 Adverse Event/Reaction

An AE is defined as "any untoward medical occurrence in a subject, or clinical investigation subject administered a pharmaceutical product, and which does not necessarily have a causal relationship with this treatment. An AE can therefore be any unfavorable and unintended sign, symptom or disease temporally associated with the use of an investigation product, whether or not related to the investigational product".

An adverse treatment reaction is an "untoward and unintended response to an IP related to any dose administered". All AEs judged by either the reporting Investigator or the Sponsor as having a reasonable causal relationship to an IP qualify as adverse treatment reactions. The expression of "reasonable causal relationship" means to convey in general that there are facts or arguments which suggest a causal relationship.

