8.3 Causality of AEs

The following system will be used by the Investigator (Global Introspection assessment) as a guiding tool to assess treatment relationship: Unrelated, unlikely, possibly, probably and certainly.

TERM	DEFINITION	CLARIFICATION			
Unrelated	Those AEs which, after careful consideration, are clearly due to extraneous causes (medical history, demography details, disease, environment, etc.)				
Unlikely	A clinical event, including laboratory test abnormality, with a temporal relationship to treatment administration which makes a causal relationship improbable, and in which other treatments, chemicals or underlying disease provide plausible explanations.	It does not follow a reasonable temporal sequence (Improbable temporal relationship) from administration of the treatment. It could also be explained by patient's concurrent disease, environmental factors, medical history and other concomitant treatments or chemicals including food-treatment interactions			

Possibly	A clinical event, including laboratory test abnormality, with a reasonable time sequence to administration of the treatment, but which could also be explained by concurrent disease or other treatments or chemicals. Information on treatment withdrawal may be lacking or unclear.	 It follows a reasonable temporal sequence from administration of the treatment. It could also be explained by patient's concurrent disease, environmental factors, medical history and other concomitant treatments or chemicals (including food-treatment interactions). There is no information or uncertainty with regard to what has happened after stopping the treatment.

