Certainly	A clinical event, including laboratory test abnormality, occurring in a plausible time relationship to treatment administration, and which cannot be explained by concurrent disease or other treatments or chemicals. The response to withdrawal of the treatment (dechallenge) should be clinically plausible. The event must be definitive pharmacologically or phenomenologically, using a satisfactory rechallenge procedure if necessary.	1. It follows a plausible time sequence to treatment intake, this means that there is a positive argument in sufficient detail to support the view that the treatment is causally involved, pharmacologically or pathologically e.g. pharmacokinetics and type of reaction. 2. It could not be explained by patient's concurrent disease, environmental factors, medical history and other concomitant treatments or chemicals including food-treatment interactions (i.e. no alternative causes). 3. It disappears or decreases in severity on cessation or reduction in dose or on administration of a specific antagonist wherever possible. 4. It is an objective and specific medical disorder or a recognized pharmacological phenomenon for instance 'grey baby syndrome' and chloramphenicol or anaphylaxis immediately after the administration of a treatment that had been given previously. This means that any other event is automatically excluded and can never qualify for 'Certain' (even in the case of a positive rechallenge observation). 5. It reappears on readministration of the treatment (only if ethically correct i.e. in case of non-serious, and easily treatable AEs).

Assessments of Unlikely and Unrelated do not meet the threshold for reasonable suspected causal relationship and are therefore classified as Unrelated for regulatory reporting and within a binary scale of Related/Not Related.

The Investigator should consider the following before reaching a decision on causality assessment:

- Time relationship between IP use and event's onset
- Medical history
- Study treatment
- Mechanism of action of IP
- Class effect
- Concomitant treatments in use
- Lack of efficacy/worsening of existing condition
- Erroneous treatment with study treatment or concomitant medication
- Protocol-related process

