4.14.1 Adverse Events

An AE is defined as “any untoward medical occurrence in a subject, or clinical investigation subject administered a pharmaceutical product, and which does not necessarily have a causal relationship with this treatment. An AE can therefore be any unfavorable and unintended sign, symptom or disease temporally associated with the use of an investigation product, whether or not related to the investigational product”.

Any relevant observations made (including physical examination findings, clinically relevant abnormal vital signs, clinically relevant laboratory abnormalities, and clinically relevant ECG findings) prior to or after administration of the single dose of IP are to be recorded on the AE eCRF. An AE relating to a pre-existing condition will only be recorded if there is a worsening of the pre-existing condition during study conduct with regard to nature, severity or frequency. An event will be considered a treatment-emergent AE (TEAE) if the start or worsening of the event was on or after the administration of IP. Summaries of adverse events will be limited to TEAEs, but listings of all events will be provided. A serious adverse event is an event recorded as ‘Serious’ on the adverse event eCRF page. Adverse events will be classified by MedDRA SOC and PT.

The overall summary of TEAEs will include frequencies and percentages and will be presented for the following:

- Overview of adverse events;
- All adverse events by SOC and PT;
- Serious adverse events SOC and PT;
- Adverse events by SOC, PT, and severity;
- Adverse events related to study treatment by SOC and PT

	CLR_17_17 Statistical Analysis Plan	
	Date: 30-Sep-2022	Page 23 of 28

An adverse event will be considered related to study drug if the relationship is “possibly”, “probably”, or “certainly”. The severity of an adverse event will be rated by the investigator as “mild”, “moderate”, or “severe”. Subjects experiencing multiple instances of the same PT are only counted once within each SOC and PT combination. Subjects experiencing multiple instances of the same PT will only be counted once according to the highest severity during the treatment emergent period when summarizing severity.

Serious adverse events, if present, also will be listed using verbatim and SOC/PT. Should any serious adverse events occur during the study, the serious adverse events are displayed in a table and a narrative for each serious adverse event included in the study report.

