Adverse Events of Special Interest (AESIs) will be summarized descriptively. AESI-related safety endpoints include:

- Percent of subjects with severe infections, defined as any infection meeting the regulatory definition of a SAE, or any infection requiring IV antibiotics whether or not reported as a serious event, as per the regulatory definition
- Percent of subjects with malignancies (excluding carcinoma in situ of the cervix)
- Percent of subjects with non-melanoma skin cancer
- Percent of subjects with melanoma skin cancer
- Percent of subjects with major adverse cardiovascular event (MACE)
- Percent of subjects with treatment-related hypersensitivity reactions (e.g. anaphylaxis, urticaria, angioedema, etc.)

All AEs will be presented in full in a comprehensive listing including subject number, treatment regimen, severity, seriousness, action taken, outcome, relationship to treatment, onset/stop and duration. Details of SAEs and AEs leading to withdrawal will be listed separately.

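### The hypersensitivity AESI counts only treatment-related reactions, so no visible planned table gives the pooled all-causality percentage by arm

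*SAP*

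**What the plan says.** SAP 4.14.1 names six AESI-related endpoints, to be summarised descriptively. Five carry no causality condition. Severe infections include "any infection requiring IV antibiotics whether or not reported as a serious event". Neoplasms appear as "Percent of subjects with malignancies (excluding carcinoma in situ of the cervix") and as separate items for non-melanoma and melanoma skin cancer. Major adverse cardiovascular events are counted as such. The sixth is "Percent of subjects with treatment-related hypersensitivity reactions (e.g. anaphylaxis, urticaria, angioedema, etc".

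The same section defines relatedness: "An adverse event will be considered related to study drug if the relationship is “possibly”, “probably”, or “certainly". Protocol 8.3 agrees: "Assessments of Unlikely and Unrelated do not meet the threshold for reasonable suspected causal relationship and are therefore classified as Unrelated" for regulatory reporting and on a two-level scale.

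SAP 4.14.1 also plans TEAE tables by SOC and PT for all events, for serious events, by severity, and for related events. A full AE listing shows treatment regimen and relationship. Within the tables a subject counts once for each combination of SOC and PT. Protocol 9.7.1 says summary statistics are shown by treatment group.

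**The concern.** In a randomised, blinded trial the placebo arms show how often a reaction would occur without the drug. If each event must first pass an individual causality judgement, some events are set aside before that comparison is read, and the row comes to depend on how strictly sites rate. The plan accepts this for hypersensitivity but for none of the other five AESIs.

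Protocol 8.2.7 defines anaphylaxis by clinical criteria, with no causality rating to the investigational product. A case that meets those criteria but is rated *unlikely* would be missing from the row meant to show it.

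What is at stake is one safety percentage in a descriptive table, but it is the grouped figure a reader would look for when asking whether MM-II causes hypersensitivity. The primary safety objective is safety and tolerability, and Protocol 4.2 states its expectation for moderate to severe AEs against placebo.

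**Working it through.** **1. What is excluded.** SAP 4.14.1 counts *possibly*, *probably* and *certainly* as related. Protocol 8.3 has two further ratings, and "Assessments of Unlikely and Unrelated do not meet the threshold for reasonable suspected causal relationship". So a hypersensitivity reaction rated *unlikely* or *unrelated* is not in the AESI percentage.

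**2. Which reactions those are.** Under Protocol 8.3, *unlikely* requires an improbable temporal relationship together with another explanation, described as: "It could also be explained by patient's concurrent disease, environmental factors, medical history and other concomitant treatments or chemicals including food-treatment interactions". An event with reasonable timing that also has another explanation is *possibly*, and is kept. The filter therefore acts mainly on timing. There is one injection and 26 weeks of follow-up, so there is room for such ratings, but the documents do not say how often they are expected.

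**3. Where the excluded reactions still appear.** They are in the all-TEAE and severity tables, in the SAE table if serious, and in the listing. Each is under its own preferred term. A subject with two different terms, say urticaria and angioedema, counts in two PT rows, so adding rows does not give a percent of subjects. An SOC row is not defined as the hypersensitivity group either. The listing holds what is needed to rebuild the count, but no visible table does so.

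**4. Size, by assumption.** The documents give no hypersensitivity rate, so there is no planned figure to reproduce. Inputs:
- Total 348 (Protocol synopsis).
- Allocation 3:3:3:1:3:1. The protocol states this for added subjects; applying it from the start is an assumption. MM-II: 348 × 9/14 = 223.7, about 224. Placebo: 348 × 5/14 = 124.3, about 124.
- Assumed true risks of 4% and 1%, and a share *r* of reactions rated related, equal in all arms.

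Expected count = n × risk × r. Difference = r × (4% − 1%). Ratio = 4r/1r = 4. Approximate standard error (SE) of the log ratio = √(1/a + 1/b − 1/224 − 1/124), with a and b the two counts.

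| r | MM-II count | Placebo count | Difference (points) | Ratio | SE of log ratio |
|---|---|---|---|---|---|
| 1 | 8.96 | 1.24 | 3.0 | 4 | 0.95 |
| 0.75 | 6.72 | 0.93 | 2.25 | 4 | 1.10 |
| 0.5 | 4.48 | 0.62 | 1.5 | 4 | 1.35 |

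With about one expected placebo event the SE formula is rough; only its growth is informative. A second assumed case, one MM-II arm against one placebo arm of 72 with risks of 5% and 2%, behaves the same way. Counts are 3.6 vs 1.4 at r = 1 and 1.8 vs 0.7 at r = 0.5, the difference falls from 3.0 to 1.5 points, and the ratio stays 2.5.

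**5. If ratings are not equal across arms.** Split the 4% into 1% background, present in every arm, and 3% caused by the drug.
- Half of the background reactions rated not related, drug-caused ones untouched: MM-II 3 + 0.5 = 3.5%, placebo 0.5%. Difference 3.0, ratio 7.
- Half of the drug-caused reactions rated not related, background untouched: MM-II 1 + 1.5 = 2.5%, placebo 1%. Difference 1.5, ratio 2.5.

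The related-only percentage can move either way, and on its own it does not show which case applies.

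**The case against.** The strongest reply is that little is lost. Every event stays in tables by arm and in the listing. A serious reaction, which would include most cases anyone would worry about, gets a table entry, a separate listing and a narrative whatever its causality. Raters are blinded (Protocol 6.4), so equal strictness across arms is the natural expectation, and then the ratio is unchanged. The filter may even help: improbable timing should pick out background allergy more than drug reactions, as in the first case of step 5. Confounded reactions with plausible timing are kept as *possibly*. And the protocol text visible here contains no AESI definition, so the origin of the restriction, or a term list behind it, cannot be checked.

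Most of this stands, and it limits the point to the AESI row. It does not supply the missing pooled percentage. The argument that the filter removes mainly background events can be tested only by showing the unfiltered and related figures together.

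Three stronger readings are tempting and should not be drawn.
- A reader might infer that these reactions vanish from the comparison between arms. The general TEAE tables and the listing show that they do not.
- A reader might infer a contradiction with Protocol 8.2.1, which says "All AEs judged by either the reporting Investigator or the Sponsor as having a reasonable causal relationship to an IP qualify as adverse treatment reactions". That defines an adverse treatment reaction in general, not this AESI, and the visible SAP rule does not say whose rating counts. No contradiction is shown, and no Sponsor rating need be required.
- A reader might infer that *unlikely* ratings are common for late urticaria or angioedema. The documents give no frequency.

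**Conclusion.** The point holds in a limited form. Hypersensitivity is the only one of the six AESIs conditioned on relatedness. Reactions rated *unlikely* or *unrelated* are omitted from its percentage and remain only under individual preferred terms and in listings. No planned table in the visible text gives the pooled percent of subjects by arm regardless of causality.

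The loss is in event count, precision and absolute difference. With equal ratings across arms, the difference shrinks in proportion to the share rated related: from 3.0 to between 2.25 and 1.5 points under the assumed 4% and 1% risks and a 25% to 50% loss. Bias in the ratio needs ratings that differ by arm. The AESI summary is descriptive, so no test or alpha is touched. This is a cheap improvement to a safety table, not a flaw that undermines the safety analysis. The textual part rests on the visible SAP and protocol; the sizes rest wholly on the assumed rates, shares and initial allocation.

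**What to change.** In SAP 4.14.1, define the item as the percent of subjects with treatment-emergent hypersensitivity reactions regardless of causality, shown by arm. Identify the events with a MedDRA term list fixed before unblinding, and include any event meeting the Protocol 8.2.7 criteria. Keep the current figure as an *of which related* sub-row under the SAP's existing definition of related.

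The cost is one changed SAP line, one added table row and the work of agreeing the term list. No new data from subjects are needed for the table. The downside is that some coincidental background allergies will be counted, in all arms; the sub-row lets a reader see how many reactions the raters set aside in each arm.

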4.14.2 Vital Signs Measurements

Vital sign observed values and changes and shifts from Baseline will be summarized at each scheduled visit, where applicable. Shifts will be presented for parameters that are further classified as “Normal”, “Abnormal Not Clinically Significant (NCS)” and “Abnormal Clinically Significant (CS)”. Abnormal NCS and Abnormal CS will be combined and displayed as “Abnormal” in the shift tables. A listing of all clinically significant abnormal results will be presented.

4.14.3 Clinical Laboratory Tests

Clinical laboratory parameters (e.g., albumin, etc.), including observed values and changes and shifts from Baseline, will be summarized at each scheduled visit, where applicable. Laboratory

	CLR_17_17 Statistical Analysis Plan	
	Date: 30-Sep-2022	Page 24 of 28

parameters may be classified as “Low”, “Normal”, or “High” (quantitative parameters) or “Abnormal” or “Normal” (qualitative parameters) by the central laboratory according to the reference ranges provided in the laboratory data transfer. “Low”, “High”, and “Abnormal” results will be flagged in the listings of individual subject data. Some parameters may not have normal ranges.

Urine drug, urine cotinine, urine alcohol, FSH, serology, coagulation, and pregnancy test results will also be presented in data listings.

4.14.4 ECGs

The overall ECG interpretation will be summarized by presenting the number and percentage of subjects with “Normal”, “Abnormal, not clinically significant”, and “Abnormal, clinically significant”. Shifts from Baseline in overall ECG interpretation will also be presented for “Normal” and “Abnormal”. A listing of all clinically significant abnormal overall ECG interpretations will be presented. Continuous ECG parameter (e.g., QTcF) observed values and changes from Baseline will be summarized per schedule.

4.14.5 Physical Examinations

Physical examination results will be summarized with incidence of “Normal”, “Abnormal NCS” and “Abnormal CS” by body system at each scheduled visit. Shifts from Baseline will also be presented by body system for “Normal” and “Abnormal”. A listing of all clinically significant abnormal results will be presented.

5. DATA HANDLING

5.1 Baseline, Pre-Dose, and Study Visits

Baseline daily VAS knee pain score will be calculated as the average of the assessments on Day 1 and the previous six days. For all other parameters, the last non-missing value, including unscheduled, of a variable taken before the single dose of IP will be used as the Baseline value. Except for determination of the PK parameters, all post-Baseline unscheduled data will be excluded from the analyses and presented in the listings only. Except for pharmacokinetic concentration data used to derive PK parameters, which will be analyzed at the actual sampling times, including unscheduled, all other analyses presented by collection day and/or by time point will be based on the schedule of assessments as planned in the protocol and recorded on the eCRFs. However, subjects who prematurely discontinue from the study having their final visit assessments collected on the Week 26 eCRFs. For these subjects, data collected under Week 26 will be mapped to one of the scheduled visits based on the following visit windows. On a per data point basis, if no scheduled result exists for the mapped visit, then the Week 26 will be used in the analysis for

that visit. If there is a scheduled result associated with the mapped visit, then the original scheduled result for that visit will be used in the analysis and the mapped Week 26 result will be presented in the listings only.

Visit	Target Study Day	Study Day Range
Week 1 ^a	8	1 – 11
Week 2	15	12 – 22
Week 4	29	23 – 43
Week 8	57	44 – 71
Week 12	85	72 – 99
Week 16	113	100 – 127
Week 20	141	128 – 162
Week 26	183	≥ 163

a: Day 2 assessments are scheduled for specific hours on that day.

Any subject discontinuing prior to Week 1 will have their early termination assessments mapped to Week 1 and not to specific hours on Day 2 regardless of the date.

5.2 Pooling of Sites

Sites contributing less than 16 subjects to the PPAS will be pooled within region (US Sites, Denmark Sites, Hong Kong Site). Pooling will begin by sorting the sites within a region based on the number of subjects in the PPAS. The site with the lowest number of subjects will be pooled with the site with the next lowest number of subjects. If necessary, pooling with subsequent sites will continue until the pooled site contains at least 16 subjects in the PPAS. Pooling for additional sites will continue until all sites/pooled sites within a region have at least 16 subjects in the PPAS. Pooled site will be used for all analyses (e.g., MMRM) containing site in the model or site as a stratification factor. If a site does not have any subjects in the PPAS, then it will be combined with the pooled site containing the greatest number of individual sites within the same region. If there is more than one pooled site with the greatest number of individual sites, then it will be combined with the pooled site with the fewest number of total subjects.

5.3 Missing Data

WOMAC A pain scores will be imputed as described in Section 4.9.1 for the sensitivity analysis based on multiple imputations. All other analyses will be based on available data. Handling of plasma values that are BQL with respect to the pharmacokinetic analyses are described in Section 4.13.

	CLR_17_17 Statistical Analysis Plan	
	Date: 30-Sep-2022	Page 26 of 28

5.4 Unscheduled Data

Unscheduled PK collections will be used for the derivation of the PK parameters. For all other data obtained from unscheduled assessments, results will only be considered for Baseline determination; otherwise, unscheduled data will not be used in summary tables or included in the analyses. All unscheduled data will be presented in the listings.

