4. STATISTICAL METHODOLOGY

4.1 General Principles

All collected study data will be presented in listings. All derivations and statistical analyses will be performed using SAS® software Version 9.4. Prior and concomitant medications will be coded using World Health Organization (WHO) Drug Dictionary Enhanced September 1, 2020. Adverse events (AEs) and medical history will be coded using Medical Dictionary for Regulatory Activities (MedDRA) Version 23.1.

Unless stated otherwise, descriptive summaries for continuous variables will include n (number of subjects with non-missing results), mean, standard deviation (SD), median, minimum, and

maximum. For categorical variables, n and percent will be provided. Percentages will be calculated out of the number of subjects in the given population with a non-missing result.

Nominal outcome summaries, presented by collection day and/or by time point, will be based on scheduled assessments as planned in the protocol. Unscheduled assessments will be presented in listings and will not be included in the analyses except for determination of Baseline as described in Section 5.1 and for the derivation of pharmacokinetic parameters. All other visit and time point collections will be as recorded on the electronic case report forms (eCRFs).

The protocol specifies that dosing with study drug will be on Day 0 with study days based on this date. In the context of the SAP and associated tables, figures, and graphs, study days from this point on will be based off of the day of dosing with the day of dosing being Day 1 and the day prior to dosing being Day -1. i.e., there will no Day 0.

Unless otherwise stated, hypothesis testing will be two-sided with an alpha level of 0.05.

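### Abnormal safety results seen only at unscheduled or displaced early-termination assessments enter no laboratory, vital sign, ECG or examination table; one worst post-baseline shift would close the gap

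*SAP*

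**What the plan says.** The exclusion rule appears three times in the SAP, and the three statements are consistent.

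- SAP 4.1: "Unscheduled assessments will be presented in listings and will not be included in the analyses except for determination of Baseline". Derivation of PK parameters is the other exception.
- SAP 5.1: apart from PK parameters, "all post-Baseline unscheduled data will be excluded from the analyses and presented in the listings only".
- SAP 5.4: "unscheduled data will not be used in summary tables or included in the analyses", followed by "All unscheduled data will be presented in the listings".

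For subjects who leave early, the final assessments are collected on the Week 26 form and mapped to a visit by study day (SAP 5.1). The rule works result by result: "if no scheduled result exists for the mapped visit, then the Week 26 will be used in the analysis" for that visit. If a scheduled result is already there, "the mapped Week 26 result will be presented in the listings only".

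Vital sign (4.14.2), laboratory (4.14.3) and physical examination (4.14.5) summaries are by scheduled visit; for vital signs, "changes and shifts from Baseline will be summarized at each scheduled visit, where applicable". The ECG section (4.14.4) summarises the overall interpretation and its shift from Baseline, and continuous values per schedule; the general exclusion applies to it too. No shift from Baseline to the worst post-dose value is described.

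**The concern.** Excluding off-schedule results is sensible for by-visit means, because it keeps one comparable value per subject per visit. It suits the detection of abnormalities less well. Unscheduled tests are often done because something looks wrong, and an early-termination visit captures the subject's state on leaving.

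Safety and tolerability at Week 12 is a primary objective. SAP Section 2 lists laboratory assessments, vital signs, ECG and physical examination as its endpoints alongside AEs, so each should support a comparison between arms in its own right. Listings keep the individual values but give no count per arm.

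**Working it through.** The documents state no figure on this point, so the check traces where a post-dose abnormal result can appear.

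**Step 1. Routes into a by-arm table.**

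- *Case 1: the abnormality is found at a scheduled visit and then repeated off schedule.* The scheduled value stays in the shift table, and only the repeat goes to listings. The abnormality is not missed.
- *Case 2: it is first found off schedule and judged clinically significant.* SAP 4.14.1 has relevant findings of all four kinds recorded as AEs, with no limit to scheduled visits. Protocol 8.2.6 makes a clinically significant result an AE if it comes with symptoms or needs further diagnostic work or intervention. The finding is then counted in the tables of treatment-emergent AEs.
- *Case 3: it is first found off schedule and is out of range or abnormal, but not judged clinically significant.* It is not an AE under protocol 8.2.6, and SAP 4.1, 5.1 and 5.4 keep it out of the shift tables. It appears in listings only.
- *Case 4: a scheduled value is abnormal and a worse one is seen off schedule.* The subject is already counted as abnormal. Unless the worse value is recorded as an AE, its extent, or a move from not clinically significant to clinically significant, is not tabulated.

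The gap is case 3, and in part case 4.

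**Step 2. Are such abnormalities meant to be in these tables?** Yes. SAP 4.14.2 merges the clinically significant and not clinically significant classes into one abnormal class for the vital sign shifts. The ECG and examination shifts also use only normal and abnormal. Laboratory results are classified by reference range (4.14.3), with no judgement of significance. At scheduled visits the shift tables therefore count abnormalities that AE reporting does not require. Case 3 results are of the same kind and are left out only because of when they were taken.

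**Step 3. When is an early-termination result displaced?** The inputs are the target days and windows in SAP 5.1. Assume each scheduled visit falls on its target day and the parameter is measured at every visit. A termination after the target day but inside the window is then displaced, so displaced days = upper window limit − target day.

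| Visit | Target day | Window | Displaced days | Days in window |
|---|---|---|---|---|
| Week 1 | 8 | 1–11 | 11 − 8 = 3 | 11 |
| Week 2 | 15 | 12–22 | 22 − 15 = 7 | 11 |
| Week 4 | 29 | 23–43 | 43 − 29 = 14 | 21 |
| Week 8 | 57 | 44–71 | 71 − 57 = 14 | 28 |
| Week 12 | 85 | 72–99 | 99 − 85 = 14 | 28 |
| Week 16 | 113 | 100–127 | 127 − 113 = 14 | 28 |
| Week 20 | 141 | 128–162 | 162 − 141 = 21 | 35 |

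Displaced days: 3 + 7 + 14 + 14 + 14 + 14 + 21 = 87. Total days: 11 + 11 + 21 + 28 + 28 + 28 + 35 = 162. Share: 87 / 162 = 54%.

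This is a share of calendar days, not of subjects. The true share depends on when subjects leave. It is lower for parameters not measured at every visit, because the early-termination result is then used. The assessment schedule is not visible, so no better figure can be given.

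**The case against.** The other side has a good case, and most of it stands.

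- **A reader might infer that off-schedule findings vanish from all safety reporting.** They do not. Tables of treatment-emergent AEs and the summaries of AEs of special interest are not tied to scheduled visits. Needing further diagnostic testing is itself one of the criteria that make a clinically significant abnormality an AE, although protocol 8.2.6 exempts errors and simple laboratory repeats. All unscheduled results are listed, clinically significant vital sign, ECG and examination results have their own listings, and out-of-range laboratory results are flagged.
- **A reader might infer that the abnormality that prompted the extra test is lost.** If it came from a scheduled visit, it is not (case 1).
- **A reader might infer that the shift tables are biased.** They correctly describe shifts at scheduled visits. Whether a subject was ever abnormal is a different quantity, which the SAP does not claim to report.
- **A reader might see unfairness in letting a pre-dose unscheduled value serve as Baseline while a post-dose one cannot show a shift.** Protocol 9.7.1 defines Baseline as the last value before dosing, and this applies equally to every arm. It is not a defect.
- **Early-termination results are largely handled.** They are used whenever the mapped visit lacks a result for that parameter.

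What does not stand is that AE reporting and listings together close the gap. Neither gives a by-arm count of off-schedule abnormalities judged not clinically significant, although the shift tables count these at scheduled visits. The SAP also shows that the problem can be met: for rescue medication, 4.10 adds a last-visit summary to capture use between the last scheduled visit and early termination. The safety parameters have no counterpart.

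**Conclusion.** This is a cheap improvement, not an error. The SAP rule is internally consistent and loses no data. An abnormality first or most severely seen at an unscheduled or displaced early-termination assessment, and not recorded as an AE, is counted in no by-arm table.

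The size cannot be estimated. The documents give no number of unscheduled tests, and the assessment schedule and the protocol text on unscheduled visits are not visible. A reader might assume some percentage and turn it into a number of subjects per arm. No document supports such a percentage, and one common arm size would not do either. Even 80 subjects in each of six arms would make 6 × 80 = 480, against about 348 planned, and the approximately 72 evaluable subjects in the synopsis refer only to Arms A, B, C and E. The 54% in the working shows only that displacement is not confined to rare dates, given visits on target days and measurement at every visit.

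The conclusion assumes that no worst post-baseline summary is planned in text that cannot be seen. Efficacy results, sample size, power and alpha are unaffected.

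**What to change.** Keep the by-visit tables on scheduled data. Then:

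1. In SAP 4.14.2 to 4.14.5, add one shift from Baseline to the worst post-baseline result for each parameter, or for each body system in the physical examination. Use all post-dose results: scheduled, unscheduled and early termination. For quantitative laboratory parameters, show the worst low and worst high separately. Where findings are graded for clinical significance, keeping the two abnormal classes apart would also show case 4.
2. Present it through Week 12 and through Week 26. Unscheduled results belong to no visit, so define the Week 12 cut by study day; Day 99, the end of the Week 12 window in SAP 5.1, is a natural choice.
3. In SAP 4.1, 5.1 and 5.4, exempt this summary from the exclusion.
4. Footnote the number of unscheduled assessments per arm.

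The cost is wording in seven SAP sections and one further table for each type of data, all from results already collected. The downside is that arms with more off-schedule testing have more chances to show an abnormal value. The table should therefore be read beside the by-visit tables, with the footnote in view.
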